Pill count			X	X	X	X		X	X	X	X
Adverse events reporting			X	X	X	X		X	X	X	
Physical exam	X		X**			X**		X**			X**
BP screening	X		X			X		X			X
Focused medical history	X										
Updated medical history			X			X		X			X
Randomization			X								
24-hr ABPM			X			X		X			X
FMD			X			X		X			X
Blood sample	X		X			X		X			X
CBC	X		X			X		X			X

Project 2: The Effects of Urate Lowering Therapy on Inflammation, Endothelial Function, and Blood Pressure (NIAMS: CORT)

Liver tests*	X		X		X		X		X	
Pregnancy test [†]	X		X		X		X		X	
Serum creatinine	X		X		X		X		X	
Serum urate	X		X		X		X		X	
hsCRP			X		X		X		X	
Cotinine	X		X		X		X		X	
Serum banking [§]			X		X		X		X	
Contact check in				X	X		2X		X	X

PE-physical examination, BP-blood pressure, ABPM-ambulatory blood pressure monitoring, FMD-flow mediated dilation of the brachial artery, hsCRP-highly sensitive C-reactive protein

*Liver tests are alanine aminotransferase, aspartate aminotransferase, and alkaline phosphatase. At screening only, a bilirubin test was performed.

** Physical exams will be conducted following screening visit only in cases where rash has been reported

[†]Only in women

^{††}Revised timeline corresponded to reduction in washout phase from 4 to 2 weeks for male participants and female participants depending on menstrual cycle.

[§]Sera and whole blood (for DNA extraction) will be stored.

Visit 1:

- Informed Consent
- Blood pressure
- Physical Exam
- Focused medical history
- Blood sample
- Urine sample
- CBC
- Liver tests-Liver tests are alanine aminotransferase, aspartate aminotransferase, and alkaline phosphatase
- Serum creatinine
- Serum urate
- Pregnancy test[†]
- Cotinine test
- Dispense placebo run-in if all qualifications are met

Visit 2 will occur 2 weeks following the screening procedures, signing of the consent form, and 2 week long (±3 days) placebo run-in period in the UAB Hypertension Clinic. For pre-menopausal women, run-in was timed so the end of the run-in will coincide with the onset of their menses and no later than day 7 of the next cycle for standardized measurements of FMD, thus run-in was typically of a 28-day duration. ⁷⁵ Compliance with placebo run-in will be assessed through pill count. Before and after each intervention phase, the markers for

the study primary (serum urate, hsCRP, endothelial function as measured by FMD) and secondary outcomes (ambulatory BP monitoring) will be collected. Other data will be collected as needed for safety monitoring.

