Women will need to be evaluated between days 1-7 of their menstrual cycles for study visits. This will be done to make FMD results comparable among women, and between women and men, since hormone levels have been shown to affect FMD results.⁷⁵ Participants will be entered into the trial and will be randomized to receive allopurinol or placebo. Neither the participant nor the Principal Investigator will know the drug assignment. This will begin Phase 1 (i.e., the first four weeks of the intervention). Randomization lists, stratified by race and gender, will be generated using a random number generator prior to the initiation of the study (i.e., in the first six months of study funding). Randomization will occur in blocks of size 2, 4, or 8 and will be stratified on sex and race/ethnicity to ensure order of treatment administration is balanced by sex and race. Randomization will occur using a random number generator. The sequence of treatment assignment will be determined by the random number generator and held by the pharmacist creating treatment arm study pill over-encapsulation. The pharmacist will maintain the master list and securely store the randomization files.

Visit 2:

- Blood pressure
- Updated medical history
- Blood sample
- Urine sample
- 24-hr ABPM
- FMD
- CBC
- Liver tests-Liver tests are alanine aminotransferase, aspartate aminotransferase, and alkaline phosphatase
- Serum creatinine
- Serum urate
- hsCRP
- Serum banking
- Pregnancy test†
- Cotinine test
- Pill count from run-in
- Potential adverse events
 - Assess any gastrointestinal symptoms, rash, or any other untoward effect
 - If potential untoward effect, study investigator will follow-up with subject

- Dispense 4 week course of allopurinol or placebo based on treatment assignment following return of the ABPM monitor

Interim visit check-in:

Between study visits, there will be four contact check-ins to encourage study compliance. These will be made by the study coordinator or research assistant. Additionally the study coordinator and/or research associate will assess the following during the call.

- Pill count
- Potential adverse events
 - Assess any gastrointestinal symptoms, rash, or any other untoward effect
 - If potential untoward effect, study investigator will follow-up with subject
 - If no untoward effects, subject will be encouraged to continue medication

Visit 3:

- Blood pressure
- Physical exam (head/neck/heart/abdomen)
- Updated medical history
- 24-hr ABPM
- FMD

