At visits 2, 3, 4, and 5, vascular endothelial function is measured by flow-mediated dilatation (FMD) of the brachial artery performed by a study investigator who is blinded to treatment assignment. In women participants, FMD is performed within the first 7 days after onset of menstrual cycle to avoid known cyclic variations in FMD.^{76,77} After an 8-hour fasting period, FMD is measured by high-resolution ultrasound with an 11-3 MHz linear-array probe (Philips HP Agilent Technologies, Sonos 5500, Andover, MA, 01810). Prior to testing, participants were asked to rest for 10 minutes in the supine position in a quiet room. Ultrasound of the brachial artery was taken at approximately 5 cm proximal from the elbow in longitudinal section on the right arm. The probe was maintained in a fixed position at a fixed angle, and baseline artery diameter is recorded for 1 minute. Blood flow was estimated by pulsed Doppler velocity, and baseline artery diameter was assessed with simultaneous ECG recording for baseline assessment at every study visit. Reactive hyperemia was induced by inflating a BP cuff around the forearm to 50 mmHg above resting systolic BP. The cuff remained inflated for a five-minute period, and then was rapidly deflated. The longitudinal image of the brachial artery was recorded continuously from 30 seconds before to 3 minutes after cuff deflation. A mid-artery pulsed Doppler signal was obtained at an < 60° angle upon immediate cuff release and no later than 15 seconds after cuff deflation to assess hyperemic velocity parameters. Ultrasound images were recorded 30 seconds before cuff deflation, and 3 minutes after cuff deflation. The five largest diameters after deflation were averaged, and FMD was expressed as the percentage increase in diameter from the baseline average measurement to the peak average dilation. Brachial arterial flow-mediated dilatation related parameters were analyzed with edge detection software and Doppler flow analyzer (Vascular Research Tools 5 Software, Medical Imaging Applications, LLC, Coralville, IA). The calculation of FMD as a percentage change utilizes the peak diameter in response to reactive hyperemia in relation to the baseline diameter, and was calculated utilizing the following equation: $\text{Flow mediated dilation (\%)} = (\text{Peak diameter} - \text{Baseline diameter}) / \text{Baseline diameter}$, and when multiplied by 100, FMD is expressed as a percent change in vessel caliber. An increase in

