All study investigators and participating coordinators will be blinded to treatment assignment. If there is a serious adverse event, then unblinding will be discussed and if deemed necessary to unblind the participant, then the ID of the unblinded participant, reasons for unblinding, name of the pharmacist and a list of whomever becomes unblinded will be kept in the study binder. The pharmacist will contact that participant's primary physician about the exposure. If necessary, the participant will be withdrawn from the study. The pharmacist will hold the randomization codes securely until the completion of the study.

12. Study Intervention

This study meets the criteria of a clinical trial but it is not a NIH-Defined Phase III Clinical Trial as defined by NIH. The UAB IDS pharmacy is responsible for the preparation and labeling of allopurinol and the placebo. Participants will be asked to take 4 weeks of allopurinol or placebo, then will crossover to the other drug (after 2-4 week washout period) and take either allopurinol or placebo for an additional 4 weeks. Allopurinol will be prescribed in 300mg tablets. At visit 2 and 4, participants will be given a 5-week (with an additional 7 days to account for variability in appt availability) supply of medication. During visits 3 and 5 study staff will count pills (any extra will be discarded) to determine compliance. Allopurinol and placebo prescriptions will be administered by the research study coordinator conducting the visit, daily doses will be administered by the participants themselves.

13. Participant Evaluations- Study timeline, visits, and procedures (See Protocol, Section F, for details on the study timeline, visit schedules, and procedures)

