For each visit, the study coordinator and staff conducting the visit will systematically enter all participant information electronically to the Research Electronic Data Capture system (REDCap). Our team has extensive experience using the REDCap system. All data will be collected in REDCap. Additionally electronic records are kept by visit. The study coordinator and project manager will review all data collected on a regular basis. This will help ensure all electronic forms are being completed correctly, are intact, and have been entered into system correctly. Lab forms provided by the research study coordinator describing the blood work to be done should be filled out at all visits (See *Appendix 3. Standard Operating Procedures* for instruction of preparation and storage of biobanked samples). If any issues arise (including, but not limited to adverse events) during the visits that prevent the participant from continuing, these will be documented and reported to the principal investigator immediately. The laboratories and visits are outlined in the study Protocol, section F.

14. Data Collection, Study Forms, and Logs

All data for this study will be collected by study staff in accordance with 21 CFR Part 11 rules and will meet all regulatory requirements. Due to the fact that data is almost always recorded directly on a CRF, we developed electronic case report forms for all data entry using REDCap. Our team has extensive experience using the REDCap system. All forms will be completed electronically in REDCap by the study coordinator(s). All REDCap forms filled out by study personnel will be considered source documents and kept electronically. All electronic forms and logs in REDCap are encrypted and password protected and hard copies can be printed if required. A detailed listing of all current study forms is below.

14a. Table 6. Study Participant Forms- Data will be collected by the study staff at each visit on study forms as described and presented below:

Form	Description	Visit administered	Instructions	Location
Informed consent	Informed consent	Screening visit	Participant reads through consent and initials each page in the box. Participant, doctor obtaining consent and study staff should all sign, date and time stamp	Appendix 1 Study Binder
Participant information/contact	Detailed contact sheet for	Screening visit	Participant is asked for	Appendix 2

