	participant and two other listed contacts		contact information for his/herself and 2 other persons	
Screening form	Ensures eligibility by cross referencing participants labs in one form, and determining that all inclusion criteria are met.	Screening visit	Completed by study staff following prescreen and initial exam. Certified by study coordinator.	Appendix 2
Exclusions form	Ensures eligibility by cross referencing participants labs in one form, and determining that no exclusion criteria are met.	Screening visit	Completed by study staff following prescreen and initial exam. Certified by study coordinator.	Appendix 2
Initial participant questionnaire including focused medical history and health	Initial data collected on participants medical history, health status, anthropometric data, status, blood pressure, heart rate, and medication use.	Screening visit	Study coordinator queries participant on his/her medical history. Entered in REDCap	Appendix 2
Interval medical history	Updates medical history of participant between visits,	Visits 2-5	Study coordinator queries participant on	Appendix 2

	blood pressure, heart rate, and medication use.		updates to medical history. Entered in REDCap	
Concomitant medication	Record of all prescribed and other the counter medication participant is currently using	Screening visit and visits 2-5	Completed by study coordinator and entered into REDCap	Appendix 2
Lab results	All study lab data entered.	Screening visit and visits 2-5	Data Obtained from UAB labs and entered by study staff into REDCap system.	Appendix 2
FMD results	Data collected during FMD procedure	Visits 2-5	Completed by [REDACTED] and entered in to REDCap system.	Appendix 2
24-hour ABPM	Data collected by ambulatory blood pressure monitor	Visits 2-5	Data downloaded from device.	Raw data files housed on secure server
Adverse event	Adverse event data entered on this form	Visits-2-5, and during follow-up phone calls	Completed by study coordinator. PIs notified within 24 hours of any adverse event	Appendix 2

14b. Table 7. Study Specific Administrative Forms, Logs, and Data Tables

Form	Description	Location
Study roster	Complete study personnel roster and signature of all members of the study team. It is the responsibility of the Principal Investigator and/or Clinical	Study Binder REDCap System

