Investigators will adhere to rigorous requirements and should retain forms and all other study documents for a period of no less than 7 years.

15. Data Management

Data management will be the responsibility of the research assistants, study coordinator, project manager and study statistician. All data will be entered into electronic case report study forms using the REDCap (Research Electronic Data Capture) system. REDCap is a secure web application for building and managing online surveys and databases. REDCap provides audit trails for tracking data manipulation and user activity, as well as automated export procedures for seamless data downloads to Excel, PDF, and common statistical packages (SPSS, SAS, Stata, R). From REDCap all data will be exported into SAS files and stored on a secure and

encrypted server or hard drive. The study statistician will oversee the data management. Data entry, editing and updating will be the responsibility of the research assistants, while tracking and corrections will be the responsibility of the entire staff. The study statistician and coordinator will train the research assistants on proper data entry in the REDCap system. All efforts will be made to ensure the data is in compliance with the UAB Institutional Review Board (IRB) policies, Good Clinical Practice (GCP) guidelines, and Federal regulations. Since this is a single site study, no data will be transmitted between sites.

15a. External Data

The UAB Arthritis Clinical Intervention Program (ACIP) and Hypertension Clinic will handle all laboratory data collection. No external data will be collected. All Serum and DNA will be processed and stored in the lab of [REDACTED] the UAB CORT co-director. Serum and DNA processing and storage will be done by so in accordance with the standard operating procedures (see Appendix 3). The study coordinator will be responsible for the labeling and transport of all blood samples. The study coordinator will collect the lab results and record in the eCRFs for each study participant.

15b. Data Entry

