1st measure - DBP (mm Hg)	
Blood Pressure 2	
Time - 2nd Blood Pressure measurement	  H:M
BP2 - Sitting pulse	
2nd measure - SBP (mm Hg)	
2nd measure - DBP (mm Hg)	
Blood Pressure 3	
Time - 3rd Blood Pressure measurement	  H:M
BP3 - Sitting pulse	
3rd measure - SBP (mm Hg)	
3rd measure - DBP (mm Hg)	
Mean SBP	 View equation
Mean DBP	 View equation

Screenshot 11. Visit 2-5 #3 – Sample collection and laboratory results

Record ID Field	888
VISIT LABS	
Blood drawn (red top, 2 purple tops, green top, SST)	 Yes  No
Blood draw - time	
Sample Tube ID	
Sent to Lab	 Yes  No
Sent to Lab - time	
Urine collected	 Yes  No
Urine collection - time	
Sample Tube ID	
Sent to Lab	 Yes  No
Sent to Lab - time	
Sample sent for serum banking (purple top, SST)	 Yes  No
Serum bank - time	
Pregnancy test	 Negative  Positive
Continine test	 Negative  Positive
Scheduled Date (from calendar)	 Today Y-M-D <small>YYYY-MM-DD</small>
Lab Results	
Alkaline Phosphatase (39-117 Units/L)	
AST (14-40 Units/L)	
ALT (10-44 Units/L)	
Hemoglobin (12-15 g/dL)	
WBC (4000-11,000)	
Platelet count (150,000-400,000)	
Serum Uric Acid (2.0-6.9 mg/dl)	
Serum Creatinine (0.4-1.2 mg/dL)	
Estimated Glomerular filtration rate (ml/min)	 View equation
Highly Sensitive C-Reactive Protein (mg/L)	

Screenshot 12. Visit 2-5 #4 – Flow-mediated dilation

Record ID Field	888
FLOW-MEDIATED DILATION (FMD)	
Performed by	
Assistant	
Start time	
End Time	

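### Blinded staff have duties that show them post-dose serum urate, the marker allopurinol is given to lower, and no masking of it is described

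*Combined protocol and SAP*

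**What the plan says.** **Who is blinded.** Section 11: "All study investigators and participating coordinators will be blinded to treatment assignment". Section F, in the Visit 2 text: "Neither the participant nor the Principal Investigator will know the drug assignment". Section F, in the FMD text, says that the measurement is "performed by a study investigator who is blinded to treatment assignment".

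**What is measured.** Section F describes the markers collected before and after each phase as "the study primary (serum urate, hsCRP, endothelial function as measured by FMD"), with ambulatory blood pressure as secondary. Table 3 schedules urate at screening and at Visits 2-5. The Visit 2-5 laboratory form (Appendix 2, Screenshot 11) has an open field, "Serum Uric Acid (2.0-6.9 mg/dl"), beside the safety labs and hsCRP.

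**Who handles it.** Section 15a: "The study coordinator will collect the lab results and record in the eCRFs for each study participant". Table 6 (section 14a), on the laboratory form: "Data Obtained from UAB labs and entered by study staff into REDCap system". Section 13: "The study coordinator and project manager will review all data collected on a regular basis"; section 14b makes that review weekly. Section L.1 gives laboratory review to the PI or a co-investigator and has the research team look at laboratory tests every two weeks.

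**How the blind is kept.** The stated means are over-encapsulation (sections G and 9), codes held by the pharmacist (sections 10 and 11) and masked analysts (section H). Section L.2 uses the term *blinded laboratory data* without defining it.

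**The concern.** Capsules and a locked code hide the label. They do not hide a laboratory value that the drug is chosen to change. Someone who sees urate before and after a phase can form a view of what the participant took in it. With two treatments and a crossover, a correct view of Phase 1 also gives Phase 2.

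The plan already treats staff inference as a threat: section 10 varies the block sizes so that staff cannot predict the next allocation. Visible urate would open another way to infer allocation.

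At stake are the steps that involve human judgement or contact once a Visit 3 result is known:

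- the Phase 2 contacts about adherence and side effects;
- relatedness of adverse events to study drug, judged by the investigator or staff (Appendix 3, part E);
- FMD acquisition at Visits 4 and 5, or later FMD reading, if the person doing it sees laboratory results. FMD is one of the listed primary outcomes.

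**Working it through.** **Text check.** The plan states no figure on this point, so the main check sets duties against blinding.

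1. *Coordinator.* Blinded under section 11; collects and records the laboratory results under section 15a; the Visit 2-5 form includes urate. The duty as written cannot be done without seeing post-dose urate.
2. *PI and co-investigators.* Blinded under sections 11 and F; review laboratory data under sections L.1 and L.2. They see urate unless *blinded laboratory data* excludes it, and the text does not say so.
3. *Project manager and wider team.* Review all data or laboratory tests (sections 13, 14b and L.1). Section 11 does not name the project manager among those blinded.
4. *FMD operator.* Stated to be blinded. A co-investigator administers all FMD studies (Appendix 3, part C), but no text says whether that person reviews laboratory results. Part C lets all investigators exchange and peer-review recordings. Section 14c says that investigator review may cover laboratory or FMD values. Overlap is allowed but not established.
5. *Masking.* Nothing says that post-dose urate is withheld, split from the safety labs or released late. The REDCap role and access limits (sections 14b and 20) do not mention urate.

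**Timing.** Visit 2 blood is taken before dosing, because capsules are dispensed only after the ambulatory monitor is returned (section F). The first informative value is therefore from Visit 3. The documents do not say when results come back, so that day's FMD may already be done. FMD acquisition at Visits 2 and 3 is not directly exposed.

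**Illustration.** Let d be the mean fall in urate on allopurinol relative to placebo, and s the SD of the within-phase change. The documents give neither, so both are assumed. With normal changes and a cut-off at d/2, the chance of a correct guess after Phase 1 is

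P = Φ((d/2)/s) = Φ(d/(2s)).

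| d (mg/dL) | s = 0.5 | s = 0.75 | s = 1.0 |
|---|---|---|---|
| 0.5 | Φ(0.50) = 0.691 | Φ(0.33) = 0.631 | Φ(0.25) = 0.599 |
| 1.0 | Φ(1.00) = 0.841 | Φ(0.67) = 0.748 | Φ(0.50) = 0.691 |
| 1.5 | Φ(1.50) = 0.933 | Φ(1.00) = 0.841 | Φ(0.75) = 0.773 |
| 2.0 | Φ(2.00) = 0.977 | Φ(1.33) = 0.909 | Φ(1.00) = 0.841 |

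Chance alone gives 0.50.

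A second set of assumptions starts from the within-person SD of a single value, 0.5 to 0.7 mg/dL, so s = √2 × SD = 0.71 to 0.99. With falls of 1.0 to 2.5 mg/dL it gives Φ(0.5/0.99) = 0.693 to Φ(1.25/0.707) = 0.961. If the true fall also varies between people with an assumed SD of 0.5 mg/dL, that range becomes 0.684 to 0.943.

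**The case against.** **No rule is broken.** Staff are blinded to assignment, and seeing a marker is not seeing the code. This stands as a limit on the claim. A reader might infer that the blind was broken or that the plan contradicts itself outright. The documents show only that the stated duties permit inference. Nor does any text give participants their urate results.

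**Section L.2 speaks of blinded laboratory data.** It does, but the term is undefined, names no analyte and may mean only data without a treatment label. It also does not change the coordinator's duty in section 15a.

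**The route to FMD is thin.** A reader might infer that the FMD result is biased. The documents do not support that. The operator is stated to be blinded, and the names and study roster that might settle the matter are redacted. The fixed probe and edge-detection software limit discretion, though they do not remove it. The FMD route therefore stays conditional.

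**The main measurements are objective.** Ambulatory readings are automated and hsCRP is an assay; neither is directly affected. No stated hypothesis compares adverse events between treatments, and non-adherent participants stay in the intention-to-treat analysis. This lowers the stakes but leaves relatedness judgements and FMD.

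**The probabilities are assumed.** True. At a fall of 0.5 mg/dL they are only about 60-69%, and entry allows urate from 4.0 mg/dL in women and 5.0 mg/dL in men. Full adherence and a well-chosen cut-off are also taken for granted.

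**It may be too late.** Section G mentions a September 2017 amendment, and the FMD methods are partly in the past tense. If the visits are finished, only disclosure remains.

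**Conclusion.** The concern holds as a gap in the design. Followed as written, the plan puts Visit 3-5 urate in front of coordinators and investigators who are meant to be blinded, and describes no masking of it. Functional unblinding from the Visit 3 result onward is possible, not proven.

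For scale only: a guess after Phase 1 would be right about 60-70% of the time for a small fall or large variability, and above 95% only for a large fall with low variability. These figures rest wholly on an assumed fall and SD and are not bounds. They describe guessing, not bias; the documents give no basis for estimating bias in FMD or any other outcome.

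This is a cheap improvement. No stated clinical rule uses post-baseline urate: it is absent from the adverse-event table (Table 8), and section I.6 rules out treating asymptomatic hyperuricemia outside the protocol.

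**What to change.** 1. Withhold Visit 3-5 urate (values after the first dose) until database lock from coordinators, investigators, and FMD operators and readers, including peer reviewers. Either the laboratory holds these results, or they are loaded into a restricted REDCap form handled by an existing role that does no visits, FMD or adverse-event attribution.
2. Keep screening and Visit 2 urate, and CBC, liver tests and creatinine at every visit, on the present route.
3. Send flagging of abnormal urate (section 15b) and reporting of urate to the Safety Officer (section L.2) through that same role. The section 11 route for unblinding after a serious adverse event is unchanged.
4. Define *blinded laboratory data* in section L.2 to match, and align the duties in sections 13, 14a, 14b and 15a and the Visit 3-5 form.
5. Section G allows prospective allopurinol and oxypurinol testing but does not say that staff receive results during the trial. If they do, treat those results the same way.
6. If Visit 3-5 urate has already been visible, state who saw it and when, say whether the FMD operator or reader did, and report it as a limitation.

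The cost is small changes to laboratory reporting and data entry. A REDCap permission change alone is not enough, because the coordinator now collects the results before entering them.
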